6.2 Secondary Endpoint

1. Participant satisfaction [Time Frame: 4 weeks]
 - a. Feedback will be collected the same day as each training visit, using a simple survey designed on Qualtrics.
2. Depression, Anxiety, and Stress Scale (DASS-21) [Time Frame: 8 weeks]
 - a. The DASS-21 consists of three self-report scales used to measure depression, anxiety and stress. This is a shortened form of the original DASS [36], which contains 42-items but shows no improvement over the 3-factor model for the 21-item scale [41]. The DASS-21 has been validated in non-clinical samples, and may even be used to measure an overall level of psychological distress [42]. In a non-clinical sample of Greek adults 18 years of age and older, the DASS-21 showed satisfactory reliability, with Cronbach alphas of 0.85, 0.84, and 0.84 for the depression, anxiety and stress scales, respectively [43]. There was also high convergent and discriminant validity of the three scales in this same sample.
3. Credibility/Expectancy Questionnaire (CEQ) [Time Frame: 1 week]
 - a. Questions on the CEQ are used to measure the credibility of an intervention and treatment expectancy in clinical studies [27]. However, due to methodological limitations of comparison groups for mindfulness meditation (e.g., waitlist control group doesn't match intervention in any

way), evaluating the credibility of the control group intervention and the expectation of benefit to participants in both groups will facilitate the design of better comparison groups than those that currently exist.

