Study Duration	
 • Each subject will undergo 4 weeks of intervention or control group training, a pre- and post-training visit, and a 1-month follow-up. • The entire study is expected to last 3 months.
Study Phases	(1) Subjects screened for eligibility and obtaining consent;
Screening	(2) Cognitive task performance, blood sample collection, surveys;
Study Treatment	(3) Four weeks of virtual training in Koru mindfulness or an age- and time-matched comparison group;
Follow-Up	(4) One-month follow up online surveys
Efficacy Evaluations	
 • Mean number of visits attended by participants and total number of journal entries.
Pharmacokinetic Evaluations	N/A
Safety Evaluations	Self-report measures of anxiety, depression, and stress will be evaluated at the beginning of each visit to determine any changes that could be in result of the intervention.
Statistical And Analytic Plan	
 • To assess the primary objective (feasibility) of the study, the primary outcome will be the count of participants in each of the 6 visits, and the number of surveys that are completed at the 1-month follow-up contact. • To assess the secondary objective (participant compliance), the secondary outcome will be measured by total journal entries submitted during the 4 weeks of intervention training.
DATA AND SAFETY MONITORING PLAN	The Co-Investigators will review participants' experiences with study procedures on a weekly basis. Meditation practice may elicit discomfort if traumatic memories resurface or the participant is experiencing high stress. The Koru teacher is trained in trauma-sensitive mindfulness and has implemented this awareness in the design of the visits. Nonetheless, the teacher will regularly check in with students to address any concerns.

BACKGROUND AND RATIONALE

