3.1 Study Design

This proposed study is a parallel assignment randomized controlled trial. Interested individuals will be initially screened for psychiatric and neurological health, medications, use of psychoactive substances, the presence of study specific contra-indications, and prior experience with meditation. Participants who meet inclusion criteria according to the initial phone-based screening will then be invited to the lab for further screening and possible participation. Upon arrival and consent, subjects will be given a urine test to screen for psychoactive drugs and a breathalyzer test to detect alcohol currently in system. Positive results will exclude participants from further participation.

Interested participants are instructed to first complete an online screening survey (through REDCap). Potential participants are then contacted for a more in-depth phone screen. When the participant comes in for the first visit, they will be screened for any current alcohol intoxication or recent substance use, followed by a mental health assessment with the Mini-International Neuropsychiatric Interview (MINI) [25]. The participant will then have blood collected by finger prick, complete the Reward-AB task, and fill out some paper surveys. During visits 2 through 5, participants will complete virtual training on either mindfulness and meditation skills, or navigating college skills. Each visit will last approximately 90 minutes, starting with the completion of a few online surveys. Visit 6 is similar to visit 1, without the health interview. Participants will be contacted one month following the date of the 6th study visit to complete online surveys.

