3.3 Study Duration, Enrollment and Number of Subjects

The entire duration of the study is expected to take no more than 3 months. About 5-6 weeks will elapse from the first visit to the 6th visit, and the inclusion of a one-month follow-up survey adds another 4 weeks, totaling a little over 2 months. Eighteen subjects are expected to be enrolled in the study, with 9 participants randomized to each of two training groups (Koru Mindfulness as the intervention training, Navigating College serving as the age- and time-matched comparison group).

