4.3 Follow- up procedures (by visits)

One month after the conclusion of visit 6, participants will be recontacted via email with a link to REDCap to complete several surveys.

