5.4 Safety Evaluations

The DASS-21 will be used to measure depression, anxiety and stress and will be administered at the beginning of each visit. Scores will be used to evaluate any within-subject changes that may prompt further review. The KM instructor will read logs daily and determine if any participant should be followed up with.

STATISTICAL CONSIDERATIONS

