6.3 Statistical Methods

The total number of eligible participants will be used as a measure of successful recruitment strategies and feasibility of enrollment criteria. The mean number of self-report training or journaling days recorded by participants and the total number of visits attended by each participant will be used as measures of compliance with study procedures. The number of times discomfort is reported by participants with any training procedure will be used as a measure of safety. A within-subjects ANOVA will be used to analyze the change in DASS-21 scores across the training visit weeks, including the total score and scores for all 3 subscales. A 1-Sided t-Test will be used to analyze the mean difference in CEQ score between the intervention and control group.

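### The 8-week time frame of the DASS-21 endpoint does not match its visit-based collection or its analysis, which is confined to the training weeks and leaves out visit 1, visit 6 and any one-month score

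*Combined protocol and SAP*

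**What the plan says.** - **Endpoint.** Section 6.2 names "Depression, Anxiety, and Stress Scale (DASS-21) [Time Frame: 8 weeks" as a secondary endpoint. Neither the start nor the end of the eight weeks is given.
- **Collection.** Section 5.4 says the DASS-21 "will be administered at the beginning of each visit". The safety row of the synopsis says the same of the self-report measures of anxiety, depression and stress.
- **Schedule.** The synopsis states "Each subject will undergo 4 weeks of intervention or control group training". Section 3.1 adds "During visits 2 through 5, participants will complete virtual training", and section 3.3 says "About 5-6 weeks will elapse from the first visit to the 6th visit". Section 3.3 then allows a further 4 weeks to the follow-up survey.
- **One-month contact.** Section 4.3 says "participants will be recontacted via email with a link to REDCap to complete several surveys". It does not name the instruments.
- **Analysis.** Section 6.3 plans a within-subjects ANOVA to "analyze the change in DASS-21 scores across the training visit weeks", for the total score and the three subscales. No other DASS-21 analysis is described.
- **Review.** Section 5.4 adds "Scores will be used to evaluate any within-subject changes that may prompt further review". Section 6.5 includes a visit-to-visit rise in DASS-21 score among its grounds for stopping an individual's participation.

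**The concern.** The DASS-21 is both a secondary endpoint and the protocol's main structured safety measure. Its time frame, collection schedule and analysis window should describe the same set of scores, and they do not. The time frame runs beyond the last visit at which collection is specified, and the analysis window closes before that visit.

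An analyst who followed section 6.3 to the letter would produce a result for the training weeks and nothing at eight weeks. If one-month scores turned out to exist, whether and how to use them would be decided after the data were in hand. The protocol itself notes that mindfulness practice can bring discomfort to people with past trauma or high stress. Whether scores have returned to their starting level, or risen, once the course is over is therefore something this pilot could usefully report to a larger study.

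**Working it through.** The only planned figure to reproduce is the 8 weeks. No power, alpha or effect size attaches to this endpoint.

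**Inputs.** Training lasts 4 weeks (synopsis). Visit 1 to visit 6 takes 5-6 weeks, and visit 6 to the follow-up survey takes 4 weeks (section 3.3). Training visits are visits 2-5 (section 3.1). One assumption is needed for the second row below: visit 2 falls 1 week after visit 1. The documents do not give that gap.

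**Which interval gives 8 weeks?**

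| Interval | Arithmetic | Result | Equals 8? |
|---|---|---|---|
| Training plus follow-up | 4 + 4 | 8 weeks | Yes |
| Visit 2 to one-month contact | (5 to 6) - 1 + 4 | 8 to 9 weeks | At the lower end |
| Visit 1 to one-month contact | (5 to 6) + 4 | 9 to 10 weeks | No |
| Visit 1 to visit 6 | as stated | 5 to 6 weeks | No |
| Training only | as stated | 4 weeks | No |

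The figure is reproduced only by counting from the start of training to the one-month contact. Counted from visit 1, eight weeks ends 8 - 6 = 2 to 8 - 5 = 3 weeks after visit 6, and 9 - 8 = 1 to 10 - 8 = 2 weeks before the one-month contact. No planned contact falls there.

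**Which scores enter the stated analysis?**

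- Scores in the ANOVA: visits 2, 3, 4 and 5, which is 4.
- Scores if given at every visit: 6. Left out: 6 - 4 = 2 (visits 1 and 6).
- Scores if also given at one month: 7. Left out: 7 - 4 = 3 (visits 1 and 6, and one month).

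Because the scale is given at the start of each visit, the visit-5 score comes before the fourth and last class. The last score analysed therefore follows three of the four classes. The first score after the whole course is at visit 6, outside the stated window.

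**Which scores are covered by review?** The review sentence in section 5.4 and the visit-to-visit criterion in section 6.5 both apply to visits, so they cover scores up to and including visit 6. Neither says whether it extends to a score returned through the emailed link.

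**The case against.** The strongest reply is that this is a loose time frame in an 18-person feasibility pilot. Section 6.4 disclaims any power analysis, the DASS-21 is secondary, and the synopsis uses the one-month contact mainly to count completed surveys. Visit 2 can also serve as a pre-training score, since the scale is completed before the first class. And the follow-up instruments may be listed in Figure 1, which is not reproduced in the text available here.

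Part of this stands. The consequence is limited to one secondary endpoint. A visit-2 score is pre-training, although under sections 3.2 and 8.1 it is taken after allocation. If Figure 1 lists the DASS-21 at one month, the collection gap closes. The analysis gap does not: section 6.3 would still leave out visit 6 and the one-month score.

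Four stronger readings are tempting, and the documents do not support them:

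- **That distress after training goes unreviewed.** Visit 6 follows training, the DASS-21 is given at each visit, and sections 5.4 and 6.5 cover that score. The open question begins after visit 6. Section 6.5 concerns stopping participation, so its silence about a contact at the end of the study is not in itself a defect.
- **That teacher check-ins and log reading cease with training.** No end date is given for them, nor for the weekly review of participants' experiences by the Co-Investigators in the synopsis.
- **That the DASS-21 is definitely not collected at one month, or that the endpoint definitely reaches that contact.** The surveys are unnamed and the time origin is unstated. Either could be so.
- **That the gap can be expressed as a share of the eight weeks.** Such a share would count time before visit 6, when scores are collected and reviewed, and it suits an endpoint measured at discrete contacts poorly. Counting scores is the better measure.

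**Conclusion.** The inconsistency is real and modest in size. An 8-week endpoint is paired with collection specified at visits ending 5-6 weeks after visit 1, and with an analysis of visits 2-5 only. Followed exactly, the plan gives no DASS-21 result at eight weeks, uses 4 of 6 visit scores (or 4 of 7 scores), and includes neither the visit-1 baseline nor any score taken after the full course.

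The count of scores rests on reading the training visit weeks as visits 2-5, which section 3.1 supports. That a one-month DASS-21 was intended is an inference from 4 + 4 = 8. It is strengthened by the satisfaction endpoint in the same section, whose 4-week frame matches the training period, but it is not stated. The conclusion does not depend on it: if no one-month score was planned, the time frame is too long for every visit on the schedule.

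This should be corrected before analysis. It does not affect the sample size, the primary feasibility endpoint or the reported retention.

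**What to change.** If a one-month DASS-21 is intended:

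1. In section 6.2, state the origin of the eight weeks (for example, the start of training) and the contact at which they end.
2. In sections 4.3 and 5.4, state that the DASS-21 is among the one-month REDCap surveys.
3. In section 6.3, add the change from visit 1 to visit 6 and from visit 1 to the one-month contact, by arm. Report it descriptively as the mean with 95% CI and individual values. With 9 per arm the intervals will be wide, so the individual values matter and no test is needed.

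If it is not intended, restate the time frame in section 6.2 as 5-6 weeks from visit 1 and extend the section 6.3 analysis to visits 1-6.

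In either case sections 4.3, 5.4 and 6.5 must be reconciled, so that the text says whether a one-month score, if collected, falls under the review in section 5.4. What that review should do with a given score is a clinical matter for the investigators.

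The cost is protocol wording and a short descriptive table. The survey contact and platform already exist. The downside is up to 21 more items per participant at one month, if the scale is not already in that set.

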6.3 Statistical Methods

The total number of eligible participants will be used as a measure of successful recruitment strategies and feasibility of enrollment criteria. The mean number of self-report training or journaling days recorded by participants and the total number of visits attended by each participant will be used as measures of compliance with study procedures. The number of times discomfort is reported by participants with any training procedure will be used as a measure of safety. A within-subjects ANOVA will be used to analyze the change in DASS-21 scores across the training visit weeks, including the total score and scores for all 3 subscales. A 1-Sided t-Test will be used to analyze the mean difference in CEQ score between the intervention and control group.

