4.4 Subject Completion/ Withdrawal procedures

Participants will be screened for drug and alcohol use upon arrival to visits 1 and 6. If the test results from a urine sample and breathalyzer are positive, subjects will be withdrawn from the study. If participants in the KM group are experiencing extreme discomfort during weeks when visits 2-6 take place, due to resurfacing of traumatic experiences, subjects will be withdrawn from the study and given resources (see attachments) to alleviate distress. Investigators may also terminate an individual's participation if the subject is uncooperative or otherwise behaves in a way that makes study personnel feel uncomfortable or unsafe.

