6.5 Interim Analysis

The study will be stopped for any individual participant if the reported level of discomfort described by the participant in their journal entries or meditation logs is considered to be more than minimal by a trained clinical psychologist (Co-PI), if their DASS-21 scores increase significantly from one visit to the next, or if they report that the study procedures themselves have contributed to any discomfort/distress.

STUDY INTERVENTION

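### The DASS-21 analysis in Section 6.3 has no group or group-by-visit term, so it cannot show whether a change could result from the intervention, and on the plain reading it omits visit 6

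*Combined protocol and SAP*

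**What the plan says.** The synopsis (Safety Evaluations) says self-reported anxiety, depression and stress are assessed at every visit "to determine any changes that could be in result of the intervention". Section 5.4 names the DASS-21 as the instrument, has it completed at the start of each visit, and adds a second use: "Scores will be used to evaluate any within-subject changes that may prompt further review". Section 6.2 lists it as a secondary endpoint: "Depression, Anxiety, and Stress Scale (DASS-21) [Time Frame: 8 weeks".

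The whole analysis is one sentence in Section 6.3: "A within-subjects ANOVA will be used to analyze the change in DASS-21 scores across the training visit weeks", covering the total score and the three subscales. The next sentence does compare the arms, but for the credibility/expectancy score only: "mean difference in CEQ score between the intervention and control group".

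Section 3.2 randomises 18 participants, 9 per group, at the end of visit 1. Section 3.1 places the classes: "During visits 2 through 5, participants will complete virtual training". Visit 6 is the post-training visit. Section 6.5 stops an individual's participation "if their DASS-21 scores increase significantly from one visit to the next", among other reasons. No section says how missing DASS-21 scores are handled.

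**The concern.** The stated purpose is to find changes that could be due to the intervention. A matched control group was randomised, which is what makes that possible. The planned test asks only whether scores change over time. First-year students' stress may well move over a semester whatever class they attend, and without a contrast between arms such shared change looks the same as an effect of training.

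Two further points affect the same sentence. If the training visit weeks mean visits 2-5, the analysis stops before the first score that follows the complete course. And a classical within-subjects ANOVA uses only people with every score, in a trial where rising scores can end participation.

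At stake is the reading of one secondary and safety measure, not the feasibility result.

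**Working it through.** **1. Purpose against method.** The purpose (synopsis) is change that could be due to the intervention. The method (6.3) is a within-subjects ANOVA over time, and it does not say whether the arms are pooled.
- Pooled: the test is of the average time trend. A shared trend is flagged, and opposite trends cancel.
- Separate by arm: there are two tests of time. Significance in one arm and not in the other is not a test of the difference between them.

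**2. Size.** The documents give no SD, effect size, correlation or alpha for DASS-21, so there is no figure of the plan's to reproduce. Assumed: alpha 0.05, 9 per arm, visits 2-5, linear change, equal correlation ρ between visits, complete data, 20,000 simulated trials per setting.

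| Scenario and test (% significant) | ρ=0.5 | 0.6 | 0.7 | 0.8 |
|---|---|---|---|---|
| Same 0.5 SD drift: pooled | 41 | 50 | 63 | 82 |
| Same drift: mindfulness (KM) arm alone | 20 | 25 | 32 | 47 |
| Same drift: exactly one arm | 33 | 37 | 44 | 49 |
| Same drift: group-by-visit | 5 | 5 | 5 | 5 |
| Opposite 0.5 SD: pooled | 3.7 | 3.2 | 3.0 | 2.1 |
| Opposite: KM arm alone | 20 | 25 | 32 | 46 |
| Opposite: group-by-visit | 40 | 50 | 64 | 82 |
| KM-only 0.8 SD: group-by-visit | 27 | 33 | 43 | 62 |

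Check against the noncentral F distribution:
- A 0.5 SD linear trend over four visits has values 0, 0.167, 0.333, 0.5, with sum of squares about their mean 0.139.
- Pooled, shared drift: λ = 18 × 0.139/(1−ρ) = 5.0 at ρ=0.5 and 12.5 at ρ=0.8. With (3, 51) df, power is 41% and 83%.
- One arm: λ = 9 × 0.139/(1−ρ) = 2.5 and 6.25. With (3, 24) df, power is 20% and 47%.
- Exactly one arm significant: 2p(1−p) = 2 × 0.203 × 0.797 = 32% and 2 × 0.466 × 0.534 = 50%.

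These agree with the table to about one percentage point. The pooled result under shared drift is a correct detection of real change; the error would be to attribute it to the intervention.

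**3. Visit window.** The scale is completed before each class, so scores at visits 2, 3, 4 and 5 follow 0, 1, 2 and 3 classes. Visit 6 is the first to follow all 4. Weekly visits 2-5 span 3 weeks of an 8-week time frame. On the same reading the visit 1 baseline is also left out. The phrase is not defined, and Section 4.4 speaks of discomfort "during weeks when visits 2-6 take place", so a wider reading is possible.

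**4. Missing scores.** If all four scores are needed and each visit is attended independently with an assumed probability a, the expected number of complete participants is 18 × a⁴:
- a = 0.85: 18 × 0.522 = 9.4
- a = 0.90: 18 × 0.656 = 11.8
- a = 0.95: 18 × 0.815 = 14.7

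Because Section 6.5 links stopping to rising scores, missingness may depend on the outcome. The section gives no numerical threshold, so any bias cannot be sized and may be small.

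**The case against.** DASS-21 sits under safety. Sections 5.4 and 6.5 use it person by person, which needs no contrast between arms. The objectives in 2.1 and 2.2 contain no DASS-21 hypothesis, and 6.4 says recruitment is solely for feasibility. A one-line methods statement may simply not mention group. For detection alone, little is lost: with a KM-only 0.8 SD change, the pooled ANOVA is significant in 24-53% of trials, close to the 27-62% for group-by-visit, and a test in the KM arm alone does better (47-89%). The completer counts rest on assumed attendance and independence between visits; if the same people tend to miss visits, more complete cases remain.

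Much of this is fair. Individual review should continue as planned, the figures are illustrative, and the visit 6 point is partly a request for clarity. But detecting a change is not attributing it, and attribution is what the synopsis asks for. Section 6.3 chose to run an inferential test on four scores of a listed secondary endpoint, and it names a group comparison for the very next measure. If group was meant to be in the model, the text still has to say so.

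**Conclusion.** The concern holds and should be fixed. As written, the DASS-21 analysis does not use the randomised control group and cannot separate an effect of training from shared change over the weeks. That follows from the text and does not depend on the simulation. Under the assumed inputs, a shared 0.5 SD drift gives a significant pooled result in 41-82% of trials, and a misleading pattern of one arm significant and the other not in 33-49%, against 5% for the group-by-visit test.

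The omission of visit 6 is the natural reading, not a certain one. The missing-data point is a gap in specification, of unknown size. The feasibility conclusions stand.

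**What to change.** Replace the DASS-21 sentence in Section 6.3 with:

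> DASS-21 total and subscale scores will be reported by group at visits 1-6, and at the 1-month contact if collected. The between-group difference at visit 6 will be estimated with a 95% CI from a linear mixed model of visits 2-6 (group, visit, group-by-visit, visit 1 score as covariate, random intercept per participant, Kenward-Roger degrees of freedom), using all available scores of all randomised participants. Withdrawals will be listed by group and reason. The result is descriptive.

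The visit 1 score precedes randomisation, so it is a proper baseline. The change costs SAP wording only, since scores at visits 1-6 are already scheduled, and it leaves the individual review in 5.4 and 6.5 untouched.

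The limits should be stated openly:
- **Precision.** A baseline-adjusted comparison at visit 6 alone (9 v 9, 15 df) gives a mean 95% CI half-width of 0.88, 0.81, 0.73 or 0.61 SD at ρ = 0.5, 0.6, 0.7 or 0.8. Approximate check: 2.131 × √(2/9) × √(1−ρ²) = 0.87 and 0.60 at the two ends. This is a guide to the mixed model's precision, not its exact performance, and it assumes complete data.
- **Power.** The four-visit group-by-visit test detects a KM-only 0.8 SD change in only 27-62% of trials, hence an estimate with an interval, labelled descriptive.
- **Class effects.** Section 1.2 caps a class at 9 and each arm has 9, so each arm is apparently a single class. Training and class effects cannot be separated by any model.

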6.4 Sample Size and Power

A power analysis is not applicable for this pilot study due to the small number of subjects intended to be recruited solely for the purpose of determining the feasibility of conducting described study procedures.

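### The only group-level DASS-21 analysis is an omnibus within-subjects ANOVA without arm, direction or interval, so it can neither attribute nor bound a worsening in the mindfulness arm

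*Combined protocol and SAP*

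**What the plan says.** The synopsis, under Safety Evaluations, has self-reported anxiety, depression and stress assessed at each visit "to determine any changes that could be in result of the intervention". Section 5.4 names the instrument: "The DASS-21 will be used to measure depression, anxiety and stress and will be administered at the beginning of each visit". Section 6.2 also lists DASS-21 as a secondary endpoint.

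Section 6.3 gives the analysis in one sentence: "A within-subjects ANOVA will be used to analyze the change in DASS-21 scores across the training visit weeks". Four outcomes are tested this way, the overall score and each of the three subscales. The section names no arm factor, contrast, significance level, interval or size of worsening that would matter. Section 6.4 adds: "A power analysis is not applicable for this pilot study". On size, section 3.3 says: "Eighteen subjects are expected to be enrolled in the study, with 9 participants randomized to each of two training groups".

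Other safety provisions exist. Section 6.3 counts reports of discomfort. Section 5.4 has the mindfulness instructor read logs daily and uses within-person score changes to prompt review. Section 6.5 stops a participant whose DASS-21 rises significantly between visits, without defining significantly.

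**The concern.** The safety question in the synopsis concerns the effect of the intervention: did distress rise because of the training, and by how much? The planned test asks something else, namely whether any visit mean differs from any other, over everyone together.

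- **No attribution.** Without an arm term, an effect of mindfulness training cannot be separated from stress that both arms share over the term.
- **No direction.** The F statistic responds equally to a fall in distress, which section 1.3 says mindfulness training may bring.
- **No size.** With at most 18 people, a non-significant F sets no limit on the worsening that could remain.

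The visits matter too. Section 3.1 says: "During visits 2 through 5, participants will complete virtual training". If the training visit weeks mean visits 2 to 5, the ANOVA omits visit 1, the only score before randomisation. It also omits visit 6, the only in-study score after the fourth class, because surveys come at the start of each training visit.

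The pilot is meant to inform a larger study (section 2.1), and its data may enter later papers. What it can say about distress should therefore be an estimate with its uncertainty.

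**Working it through.** The plan states no power, effect size or significance level, so there is no figure of its own to reproduce.

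**Inputs from the documents.** 18 participants, 9 per arm (3.3); four training visits (3.1); DASS-21 at every visit (5.4).

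**Assumptions.** Two-sided 0.05; a 0.5-SD rise as the harm of interest; between-visit correlation ρ from 0.3 to 0.8; equal correlation between all visits; complete data. Section 6.2 gives only Cronbach alphas, which are not between-visit correlations.

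**Power of the ANOVA.** With scores in SD units, the noncentrality is λ = n·S/(1−ρ), where S is the sum of squared deviations of the visit means from their average. Degrees of freedom are 3 and 17×3 = 51.

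- Linear rise (0, 1/6, 1/3, 1/2): S = 2(0.25² + 0.0833²) = 0.139.
- Step halfway (0, 0, 1/2, 1/2): S = 4×0.25² = 0.25.
- If only the 9 mindfulness participants rise, the pooled means move half as far, so S is divided by 4: 0.0347 and 0.0625.

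Example: all 18 rise linearly, ρ = 0.5, λ = 18×0.139/0.5 = 5.0, power 41%.

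| Who rises, pattern | ρ = 0.3 | 0.5 | 0.7 | 0.8 |
|---|---|---|---|---|
| All 18, linear | 30% | 41% | 64% | 83% |
| All 18, step halfway | 51% | 67% | 89% | 98% |
| Mindfulness arm only, pooled test, linear | 10% | 13% | 19% | 27% |
| Mindfulness arm only, pooled test, step halfway | 15% | 20% | 31% | 46% |

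Simulation agrees for the all-18 rows. For the arm-only rows the formula is slightly generous, because the unmodelled arm difference adds to the error term. At ρ = 0.8, simulation gives 24% (linear) and 40% (step) instead of 27% and 46%. If visits 1 and 6 are included, the arm-only formula range becomes 10% to 56%.

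A group-by-time interaction test has almost the same power as the arm-only rows, so adding an arm term without an interval would not be enough.

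**What an interval would show.** One-sided 95% upper bound if the observed change is zero:

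- Within the mindfulness arm: t(0.95, 8)×√(2(1−ρ)/9). At ρ = 0.5 this is 1.860×0.333 = 0.62 SD.
- Between-arm difference in change: t(0.95, 16)×√(4(1−ρ)/9). At ρ = 0.5 this is 1.746×0.471 = 0.82 SD.

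| | ρ = 0.3 | 0.5 | 0.7 | 0.8 |
|---|---|---|---|---|
| Within mindfulness arm (n = 9) | 0.73 | 0.62 | 0.48 | 0.39 |
| Between arms (9 v 9) | 0.97 | 0.82 | 0.64 | 0.52 |

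**Effect of individual stopping.** Section 6.5 gives no threshold. Purely for illustration, suppose a visit-to-visit rise above 1 SD ends participation. I simulated 9 people over four visits with a true linear 0.5-SD rise and ρ of 0.5 to 0.8, either equal between all visits or decaying with distance. Mean change among those who reach the last visit is then only 0.06 to 0.44 SD, and the nominal 95% upper bound covers the true value 82% to 92% of the time. Counting each stopped participant's last score gives mean changes of 0.48 to 0.67 SD and coverage of 96% to 99%.

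**The case against.** Several points on the other side stand.

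- **The plan draws no safety conclusion from the p-value.** A reader might infer that a non-significant ANOVA would be reported as absence of harm. No section says so. The measure that 6.3 itself labels as safety is the discomfort count, and log review and individual stopping add protection. The gap is narrower: none of these estimates or bounds the mean DASS-21 change, and nothing in the plan rules that reading out.
- **The test does not generally miss a 0.5-SD rise.** A reader might infer that it usually does. If everyone rises, power passes 50% at a correlation of about 0.60 for a linear rise and about 0.28 for a halfway step. The statement fits only a rise confined to the mindfulness arm, tested in the pooled data over four visits.
- **Section 6.3 names a method, not a report format.** Visit means may well be shown beside the F-test, and they would show direction. Pooled means would still not separate the arms, and no interval is promised.
- **A bound within the mindfulness arm alone would not be enough.** It does not answer the attribution question, and it would be too reassuring if it left out people stopped for rising scores. The fix has to cover both.
- **This is a feasibility pilot that sets power aside.** That argues against a larger sample. It also favours estimation over testing.

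**Conclusion.** The concern holds in limited form. As written, 6.3 cannot attribute a DASS-21 worsening to mindfulness training or limit its size, although the synopsis uses these scores to look for changes caused by the intervention.

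For a 0.5-SD rise confined to the mindfulness arm, the pooled four-visit test has about 10% to 46% power. If all 18 rise, power is 30% to 98%, so no general claim of low power is justified. Both ranges rest on the assumed effect, correlations of 0.3 to 0.8, linear or halfway-step patterns, equal correlation between visits and complete data. Correlation that decays between visits lowers power: for all 18 rising linearly, it is 32% and 44% at adjacent correlations of 0.5 and 0.7.

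The absence of an arm term, direction and interval can be read directly from 6.3 and depends on none of these assumptions. It does not threaten the feasibility aims, but it should be corrected because the remedy uses data already planned.

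**What to change.** In 6.3, for the DASS-21 total and each subscale:

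1. Make the main summary the mean change from visit 1 in each arm and the mindfulness-minus-control difference in change, each with a 95% confidence interval or a one-sided 95% upper bound. Name in advance the visit to which the main change is measured.
2. Use all collected scores, including the last score of any participant who is stopped, and report the number stopped by arm.
3. State that a non-significant test will not be reported as evidence of no worsening.
4. Keep the ANOVA, if wanted, as a supplement, and say which visits it includes.

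The cost is a few sentences and no new data, participants or procedures. The downside is a less comfortable statement. With 9 per arm, even zero observed change would leave upper bounds of about 0.39 to 0.73 SD within the mindfulness arm and 0.52 to 0.97 SD between arms, for correlations from 0.8 down to 0.3 and complete data. A 0.5-SD excess rise could not be excluded by the between-arm bound anywhere in that range.
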